**I. Abbreviations/Acronyms**

ASL- Arterial Spin Labeling  
AE- Adverse Event  
CBF- Cerebral Blood Flow  
CP- Cerebral Perfusion  
CRF- Case Report Form  
CRU- Clinical Research Unit  
DEXA- Dual Energy X-Ray Absorptiometry  
DMC- Data Monitoring Committee  
ECG- Electrocardiogram  
eCRF- Electronic Case Report Form  
HERC- Human Exercise Research Core  
IR- Insulin Resistance  
IV- Intravenous  
MR- Magnetic Resonance  
MRI- Magnetic Resonance Imaging  
NSAID- Non-Steroidal Anti-Inflammatory Drug  
OGTT- Oral glucose tolerance test  
PC VIPR- Phase-Contrast Vastly-undersampled Isotropic Projection Reconstruction  
REDCap- Research Electronic Data Capture  
RPM- Revolutions Per Minute  
SAE- Serious Adverse Event  
SOP- Standard Operating Procedure  
VCO2- Carbon Dioxide Production  
VO2- Oxygen Consumption  
WIMR- Wisconsin Institute of Medical Research

**1. PROJECT SUMMARY**

One in five American adolescents are obese, and many of these patients exhibit some level of insulin resistance (IR). IR is associated with cerebrovascular disease, reduced memory, attention, and cognition, but how IR contributes to these in the course of adolescent brain development is unclear. The goal of this proposal is to investigate the extent and by which IR drives reductions in neurocognitive function and cerebral blood flow (CBF) in adolescents at elevated risk for poor brain and cerebrovascular health. We are testing the overall hypothesis that neurocognitive decline is linked to the severity of IR, as are reductions in brain perfusion, due to dysfunctional insulin signaling. We propose to study acute CBF control in healthy adolescents (12-18 years) across a range of IR (diabetes excluded) in collaboration with expert childhood neuropsychologists who lead a comprehensive cognitive testing protocol. Next, two complementary MRI methods (ASL and phase contrast MRI), along with a physiologic stressor to challenge CBF, will be used to test whether the impact of IR on brain macrovascular CBF and microvascular perfusion is regionally specific, with more negative effects in temporal and parietal lobes. These lobes are some of the initial brain areas to change in neurodegenerative diseases, and are involved in attention, memory, learning, and cognition. Finally, this study tests whether the degree of cognitive decline is linked to the CBF stress response and to severity of IR, and to what extent brain hypoperfusion mediates the IR-driven lower cognitive function. This study will provide the first comprehensive look at IR in adolescent brains, by utilizing extensive neuropsychological testing and state-of-the-art MR imaging, and drawing on interdisciplinary collaborations between developmental neuropsychologists, vascular physiologists, and pediatric endocrinologists. These studies are designed to uncover fundamental relationships between IR, neurocognitive function, and CBF in these blossoming adolescent brains. Exciting preliminary data support the aims—particularly uncovered by a physiologic insulin surge—signifying these findings will serve as a foundation for prospective, mechanistic studies to reduce the burden of IR and improve brain and cognitive health in this clinically important population.

## 2. SIGNIFICANCE

### 2.1. Synopsis

One in five American adolescents is obese. Up to half of those are already exhibiting insulin resistance (IR), a hallmark of metabolic syndrome and diabetes linked to serious life-altering health disorders, including cardiovascular and cerebrovascular disease. In adults, IR negatively affects brain structure and function and is reflected in lower regional brain volumes, perfusion, increased white matter hyperintensities and abnormal neuropsychological status, especially affecting memory and attention—all changes associated with accelerated cognitive and brain aging and increased risk of dementia. In an analogous fashion, a limited set of literature suggests adolescents with IR exhibit similar brain changes during maturation. We posit then that the brains of obese adolescents are more susceptible to insults of IR during rapid brain development, positioning them on an abnormal cognitive trajectory, and predisposing them to issues related to learning, behavioral stress responses, and depression.

While the metabolic consequences of IR are well described in adolescence, the impact of IR on their neurocognitive status (intelligence, memory, attention, executive function, processing speed) and cerebrovascular function and their interactions remains largely unexplored. This is important since in addition to its classic role as a metabolic hormone, insulin acts as a vasodilator and supports neurotrophic signaling in healthy humans. Therefore, dysfunctional insulin signaling may hold tremendous influence over brain health in adolescents during this vital period of brain development. New insight is required to understand where, when, and how IR negatively transforms brain health, including whether a dose-response exists between IR severity and anomalies in brain and cognition.

The **long-term** goal of this research program is to determine the influence of IR on brain development in adolescents through the relationships between neurocognition and cerebral blood supply. The **primary goal of the current project** is to quantify fundamental neurocognitive and cerebrovascular function in relation to the severity of IR. **Our central hypothesis** is that as IR worsens: **a**) subtle but meaningful neurocognitive declines emerge; **b**) regional brain perfusion is reduced primarily in areas linked to learning and memory *despite* preserved resting global cerebral blood flow (CBF); **c**) acute insulin surges exacerbate regional hypoperfusion, and **d**) cognitive scores will be lower, mediated in part by insulin-stimulated hypoperfusion.

### 2.2. Detailed Rationale

Approximately one in five U.S. adolescents (12-19 years old) suffer from obesity (15, 32) and as many as half of those may suffer from insulin resistance (IR). IR is associated with reduced regional brain volumes, connectivity, perfusion, as well as cognitive deficits (46, 49, 52). Adolescents with IR also exhibit additional cardiovascular risk factors including hyperglycemia and hypertension, which are known to increase the risk and severity of cerebrovascular and neurocognitive diseases in adults (3, 17, 30, 35, 43). Exactly how IR influences the relationship between brain perfusion and neuronal function in adolescence is undetermined. To limit the potential future social, financial and health burdens associated with IR, these children and their physicians need new options, from new research directions, to ensure healthy brain development as they grow into adults.

Adolescence is marked by a proliferation of synapses with subsequent synaptic elimination (i.e. pruning) along with increases in white matter formation and concomitant decreases in grey matter density (1, 6), primarily in the prefrontal and parietal cortices. Emerging evidence suggests adolescents with IR exhibit reduced brain volumes and connectivity, temporally associated with changes in cognitive abilities, particularly related to reductions in executive function (5). Insulin signaling pathways are important to neuron growth and development (2, 3, 7, 8, 18, 22, 31), and insulin transport into the brain is dysfunctional

in subjects with IR (30). Consistent with insulin's vital role in brain health, intranasal insulin increases brain perfusion (38), and in older adults with IR intranasal insulin improves cognitive outcomes (9). In the rapidly proliferating adolescent brain, disrupted insulin delivery or transport foretells of harmful lifelong impacts of IR on brain and cognitive development. In adolescents, a key question is whether worsening IR contributes to an abnormal neurocognitive trajectory.

Despite the associations of IR with poor brain health, the cerebral blood flow (CBF) response to acute insulin surges in humans remains largely unexplored. In healthy blood vessels, insulin evokes vasodilation via endothelial nitric oxide synthase (NOS) activation. However, insulin also induces the potent vasoconstrictor, endothelin-1, and IR shifts the balance between NOS and endothelin-1, promoting vasoconstriction (20, 21, 55). More importantly, NOS becomes "uncoupled", producing high levels of reactive oxygen species (ROS) (20, 21, 55). Excessive ROS damages the neurovascular unit coupling blood supply to metabolism, and drives neuronal dysfunction (19, 21). In adolescents with IR, a key question is whether cerebrovascular dysfunction exists at all, and its relationship to neurocognitive abnormalities at this vital stage of brain development.

In summary, insulin acts as an endocrine hormone, a neurotrophic signal, and a vasodilator, so it is logical that dysfunctional insulin signaling plays a pivotal part in linking cerebrovascular and cognitive complications in IR (10). These adolescents are particularly vulnerable, as IR occurs during critical stages of neurological development, and they present cardiovascular complications earlier in life and for a longer duration (29). Detecting neurocognitive and cerebrovascular dysfunction in its earliest stages in adolescents will provide the best opportunities to preserve or restore brain function. Addressing the questions posed above, by using dynamic testing, will begin to fill a vital knowledge gap, by concentrating on essential aspects of when, where, and how adolescent IR cultivates cerebrovascular and neurocognitive dysfunction.

### 2.3. Innovation

Many youth-focused brain studies emphasize a sole aspect of brain structure, cognitive function, or CBF. A limitation of intriguing, but associative studies is that they assess effects of IR on resting measures in adolescence, obscuring insight into the daily impact of insulin on brain health (26, 37). These resting associations lack high resolution in terms of mechanistic insight, and thus add fuel to a classic chicken or egg question: Does vascular dysfunction or neural dysfunction dominate the *earliest* brain changes in adolescents with IR? To address several limitations, this proposal combines three unique areas of innovation. First, this proposal combines collaborative expertise in pediatric neuropsychology, pediatric endocrinology, and vascular physiology to address the complexities and subtleties of the preclinical disease process. A second innovation stems from combining two powerful, complementary brain-imaging approaches that quantify brain perfusion and identify the regions most impacted by IR. **Phase-Contrast Vastly-undersampled Isotropic Projection Reconstruction, (PC VIPR)** is a high-resolution, 4D flow approach used to quantify macroscopic CBF in *all* major extracranial and intracranial arteries. Arterial Spin Labeling (**ASL**) measures provide insight into microvascular cerebral perfusion allowing identification of focused brain regions impacted by IR. No single measure of flow or perfusion can comprehensively assess cerebrovascular function in health or IR; the combination of both MRI approaches will greatly enhance insight into CBF regulation in adolescence. Third, clinically relevant insulin surges acutely stress brain blood flow regulation, highlighting cerebrovascular dysfunction that is not apparent at rest. Indeed, we present novel pilot data indicating significant neurocognitive decline along with remarkable cerebrovascular dysfunction, both of which are related to the severity of IR. When combined, the technical and conceptual innovations in this proposal will deliver novel insight into the severity and regional impact of IR on brain health and cognition in adolescents.

### 3. SPECIFIC AIMS AND PRELIMINARY EVIDENCE

Pilot studies in Aim 1 were conducted in 7 adolescents (mean age 14.7 years); 3 with low IR (HOMA-IR ~3.4) and 4 with high IR (HOMA-IR ~4.6). Five of these 7 were studied for Aims 2 and 3 (2 with low IR, 3 with high IR).

These data were collected from the awarding of a previous UW Graduate School Fall Competition Grant under IRB# 2014-0529.

#### 3.1. Aim 1

To test the hypothesis that adolescents with higher IR will demonstrate subtle but clinically meaningful neurocognitive dysfunction, primarily in the domains intelligence, memory, attention, executive function, and processing speed.

##### 3.1.1. Rationale

Associations between cognition and IR have not been extensively studied and reports are mixed on whether IR is associated with cognitive abnormality (24, 42). A handful of studies suggest youth with obesity and IR demonstrate deficits in executive control processes (e.g. attention, memory) and lower overall intelligence (46, 47). Although IR has been postulated as being a mediator for such cognitive deficits (46, 49), the association between systemic IR and cognition has not been well established in adolescents (47, 48).

##### 3.1.2. Preliminary Data

Pilot data indicate similar brain and hippocampal volumes between groups (2.93 vs 2.84 mm^3). Cognitive testing results did not differ significantly between groups. However, episodic memory, executive function, and attention, as well as total composite cognition scores were all quantitatively lower in adolescents with high IR. Notably, these smoldering decreases in cognition are directly correlated to HOMA-IR. Collectively, these data suggest brain structure remains intact at this stage, yet fundamental memory and attention measures are declining in relation to worsening insulin resistance.

#### 3.2. Aim 2

To test the hypothesis that adolescents with higher IR:

- a) exhibit intact resting global macrovascular CBF but reduced microvascular perfusion in key brain areas involved in cognition, memory, and learning
- b) will exhibit further perfusion reductions in response to an endogenous insulin surge in contrast to increased perfusion in healthy adolescents.

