### 3.2.2. Preliminary Data

First, total CBF is remarkably similar between groups (PC VIPR). However, adolescents with high IR exhibit reduced basal microvascular CP in numerous brain regions, including those involved in cognitive processing (ASL). The combination of MRI approaches suggests an uncoupling of macro and microvascular flow (17) (34), consistent with early but subtle *basal* microvascular dysfunction in IR. Therefore, it is crucial to look at both CBF and CP measures, as regional regulation appears to be differently affected by IR.

Second, following OGTT, regional CBF and CP patterns change markedly. Despite similar increases in plasma glucose, insulin increases much more in adolescents with high IR. CBF through the Middle Cerebral Artery (MCA) increases in adolescents with low IR but *decreases* in adolescents with high IR. Similar patterns were observed in the Anterior Cerebral Artery (ACA, not shown). Third, 45 minutes into OGTT, select regions increased CP in adolescents with low IR, but *decreased* CP in adolescents with high IR. Notably, many of these regions are downstream of the MCA and ACA and are linked with executive function, memory, and learning abilities. These data strongly support the hypothesis that adolescents with high IR demonstrate overt brain endothelial dysfunction, which decreases brain perfusion under the physiologic stress of hyperinsulinemia and hyperglycemia.

In summary, the combination of PC VIPR and ASL MRI approaches allow us to quantify dynamic CBF/CP responses, identify brain regions most sensitive to insulin vasodilation, and most impacted by IR. Preliminary data for Aim 2 OGTT evokes hypoperfusion occurring primarily in anterior brain regions associated with executive function and memory. In the context of insulin-driven ROS production (20, 21), and lower cognition scores (Aim 1), these data are consistent with the hypothesis that acute brain hypoperfusion, via daily insulin surges, plays an essential role in the early pathology of cognitive dysfunction in adolescents with high IR.

## 3.3. Aim 3

To test the hypothesis that higher IR is associated with lower cognitive function (Aim 1) in such a way that perfusion at rest (Aim 2A), and perfusion changes during insulin surge in particular (Aim 2B), mediate the relationship.

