##### 4.1. Subject Population

Fifty-five (55) otherwise healthy adolescents, post-puberty, between 12-18 years of age inclusive.

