#### 8.3.2. Aim 2A

Total CVC will be predicted from HOMA-IR and the covariates (intracranial volume is an additional covariate for CVC analyses). Resting CP data indicate reduced perfusion in several anterior brain regions. Pilot data yielded a correlation between HOMA-IR and resting  $\text{CVC}_{\text{MICRO}}$  of  $-0.324$ , such that a sample of size **N=55** will yield the power of 0.8 in a one-tailed test of the correlation, with Type I error rate of 0.05. In contrast, we will test, but do not expect, resting  $\text{CVC}_{\text{MACRO}}$  to be related to HOMA-IR, since resting  $\text{CVC}_{\text{MACRO}}$  is similar in low and high IR.

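### Aim 2a hypothesises intact resting macrovascular flow, but the only planned evidence is an association test expected to be null, and non-significance at N=55 would not by itself support that claim

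*Combined protocol and SAP*

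**What the plan says.** The macrovascular half of Aim 2a is a claim of no effect. Section 3.2 states it as part of the hypothesis to be tested: adolescents with higher insulin resistance "exhibit intact resting global macrovascular CBF but reduced microvascular perfusion in key brain areas involved in cognition, memory, and learning". The central hypothesis in section 2.1 repeats it, with regional perfusion reduced despite "preserved resting global cerebral blood flow (CBF").

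The analysis of this half takes one sentence in section 8.3.2: "In contrast, we will test, but do not expect, resting" CVC_MACRO to be related to HOMA-IR. The reason given is that resting values are similar at low and high insulin resistance. That rests on the pilot work in section 3.2.2 ("First, total CBF is remarkably similar between groups (PC VIPR")), and section 3 gives its size: "Five of these 7 were studied for Aims 2 and 3 (2 with low IR, 3 with high IR").

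The effect size, sample size and power in 8.3.2 belong to the microvascular measure only: r = -0.324, N = 55, power 0.8, "in a one-tailed test of the correlation, with Type I error rate of 0.05". Section 8.5 repeats 0.8 for Aim 2A with no separate macro figure. No sidedness is given for the macro test.

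**The concern.** An association test can give evidence of a relation. When it is non-significant, it does not show that the relation is absent or small. With no margin or interval rule, readers of the results would have only a p-value from which to judge whether flow is intact.

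The stake is the dissociation. Section 3.2.2 reads the pilot pattern as an uncoupling of macrovascular and microvascular flow, and section 8.3.1 gives that pattern as the reason for testing both levels. If both were reduced equally and only the micro test reached significance, the results would look like the hypothesised pattern. One significant and one non-significant test do not show that two slopes differ.

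**Working it through.** **Inputs from the documents**
- N = 55 (section 4.1). Enrolment continues until 55 complete (4.1.3), so 55 is taken as analysable.
- r = -0.324, one-tailed alpha 0.05, power 0.8, micro measure only (8.3.2).
- Covariates: five (opening of section 8) plus intracranial volume (8.3.2), so k = 6.

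**Assumptions, not in the documents**
- -0.324 is the true partial correlation for both measures.
- The macro-micro correlation lies between 0 and 0.7.
- The macro test is one-tailed or two-sided; both are shown.
- The equivalence margins are illustrative.

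**1. The plan's own figure.** Noncentral t without covariates: ncp = 0.324 × √55 / √(1 - 0.324²) = 2.54, df = 53. Power is 0.806 and the minimum N is 55, so the stated figure reproduces. The exact bivariate-normal calculation gives 0.790. With six covariates the exact power is 0.746.

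**2. Chance that the macro test misses a true -0.324 (k = 6).** One-tailed: 1 - 0.746 = 0.254. Two-sided: 0.37. Fisher z check: SE = 1/√(55 - 3 - 6) = 0.1474 and atanh(0.324) = 0.3361, ratio 2.280. One-tailed miss = 1 - Φ(2.280 - 1.645) = 0.263. Two-sided miss = 1 - Φ(2.280 - 1.960) = 0.375. At a true correlation of -0.20, the Fisher z miss rates are 0.61 and 0.72.

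**3. Chance of the false dissociation.** This is the joint event of micro significant (one-tailed) and macro not, with both true correlations at -0.324. Simulated with six degrees of freedom removed for the covariates:

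| Assumed macro-micro correlation | Macro one-tailed | Macro two-sided |
|---|---|---|
| 0 | 19.5% | 28% |
| 0.3 | 16% | 24% |
| 0.5 | 14% | 21% |
| 0.7 | 10% | 18% |

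**4. What a non-significant result would leave open.** Take an observed partial r of -0.15, one-tailed p = 0.15. The 90% CI is tanh(-0.1511 ± 1.645 × 0.1474) = -0.37 to 0.09. It includes zero and also the plan's micro effect.

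**5. What N = 55 could show with an interval rule (true r = 0, k = 6).** For margin m, the chance that the 90% CI lies inside ±m is 2Φ(atanh(m)/SE - 1.645) - 1, floored at 0. The chance that it excludes a reduction beyond m is Φ(atanh(m)/SE - 1.645).

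| Margin | CI inside ±m | CI excludes a reduction of m |
|---|---|---|
| 0.20 | 0.000 | 0.394 |
| 0.25 | 0.070 | 0.535 |
| 0.30 | 0.350 | 0.675 |
| 0.324 | 0.474 | 0.737 |
| 0.40 | 0.781 | 0.890 |

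The smallest margin with 80% power is about 0.41 two-sided, or 0.35 if only a reduction has to be excluded.

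**6. CBF versus CVC.** The hypothesis is about CBF, but the planned test uses CVC = CBF / mean arterial pressure (8.3.1), and that section puts pressure differences at up to 15 mmHg across the insulin-resistance spectrum. If pressure were 80 mmHg at one end (an assumption) and 95 at the other, equal CBF would give a CVC ratio of 80/95 = 0.84, or 16% lower. A test on CVC alone therefore does not answer a question about CBF.

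**7. Direct comparison of slopes.** Steiger approximation, one-sided, true correlations 0 (macro) and -0.324 (micro), k = 6: power is about 48%, 73% and 90% for macro-micro correlations of 0, 0.5 and 0.7.

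**The case against.** The strongest reply is that the plan nowhere writes a rule that p > 0.05 means intact. That is correct. Section 8.3.2 says only that the relation will be tested and is not expected. A reader might infer a written decision rule, but the documents do not contain one. The gap is that they do not say how intactness would be judged.

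It can also be said that no later analysis depends on a null macro result. This stands too: section 8.3.3 opens follow-up tests if either total CVC test is significant, and section 8.4 carries both measures forward as mediators. A wrong call of intact flow would affect what is claimed and would block no analysis.

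A reader might take the 25% miss rate as the chance of a false dissociation. It is not. The false dissociation also needs the micro test to succeed, which brings it to 10-20% with a one-tailed macro test. Section 8.3.1 describes the two levels as physiologically related, so some positive correlation is plausible, which favours the lower part of that range; its size is not given.

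A reader might also conclude that 55 participants can provide no evidence of intact flow. The calculations do not support that: an interval with a pre-stated margin can exclude large effects.

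The reply does not remove the main point. Intactness is stated as a hypothesis in two places, and the plan provides no analysis that could support it.

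**Conclusion.** The point holds as an inferential gap in Aim 2A. The macrovascular half is a no-effect hypothesis paired with a test that can only detect an effect, and a non-significant result at N = 55 would not by itself support it. A clearly significant macro reduction would still count against the hypothesis, so the test is informative in that direction.

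The false dissociation would occur in roughly one study in ten to one in five with a one-tailed macro test, and 18-28% with a two-sided one. This rests on a true partial correlation of -0.324 for both measures, a figure from a five-person pilot, and on an assumed macro-micro correlation. If macro flow is truly unrelated to HOMA-IR, a 90% CI would lie inside ±0.324 about 47% of the time and would exclude a reduction of that size about 74% of the time. N = 55 can therefore give limited evidence, against large effects only.

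**What to change.** In section 8.3.2:
- State the sidedness of the macro test.
- Report the adjusted resting macro association with its 90% CI, for total CBF (already defined in 8.3.3, and the quantity in the hypothesis) as well as for CVC_MACRO.
- Describe macro flow as intact only if the CI excludes a reduction beyond a margin that the investigators justify and state before analysis. The pilot value of 0.324 is used above for illustration and is a poor default, because it would allow macro flow to fall by almost the whole micro effect and still be called intact. If the CI does not exclude the margin, write that no association was detected and the result is inconclusive.
- Do not infer a macro/micro dissociation from one significant and one non-significant test. Base it on a direct comparison of the two standardised slopes, with a CI.

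The cost is a few sentences, one extra model and one contrast, with no new participants, scans or visits. The downside is that at N = 55 the answer may be inconclusive.
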